3.1.2 Treatment after Disease Progression

During the study, patients who meet criteria for disease progression per RECIST v1.1 and show evidence of clinical benefit may continue study treatment for up to 13 cycles of treatment, at the investigator's discretion, provided that the patient meets all of the following criteria:

- Evidence of clinical benefit, as assessed by the investigator
- Absence of metastatic disease
- Absence of symptoms and signs (including worsening of laboratory values (e.g., new or worsening hypercalcemia) indicating unequivocal progression of disease

- No decline in ECOG Performance Status that can be attributed to disease progression

3.1.3 Independent Data Monitoring Committee

An iDMC will be formed to evaluate safety during the study.

The safety data will include patient disposition, demographic data, adverse events, and relevant laboratory data. All summaries and analyses by treatment arm for the iDMC review will be prepared by an external independent Data Coordinating Center (iDCC). Following the data review, the iDMC will provide a recommendation as to whether the study may continue, whether amendment(s) to the protocol should be implemented, or whether the study should be stopped. The final decision will rest with the Sponsor, taking into consideration the iDMC's recommendation.

Members of the iDMC will be external to the Sponsor and will follow a separate iDMC Charter that outlines their roles and responsibilities, as well as a detailed monitoring plan.

Any outcomes of these safety reviews that affect study conduct will be communicated in a timely manner to the investigators for notification of the Institutional Review Boards/Ethics Committees (IRBs/ECs).

3.2 END OF STUDY AND LENGTH OF STUDY

The end of study will occur when all of the following criteria have been met:

- The required number of deaths for the final analysis of OS has been observed (see Section 6.5.1).
- The last patient, last visit has occurred.

In addition, the Sponsor may decide to terminate the study at any time. If the Sponsor decides to terminate the study, patients who are still receiving study treatment or undergoing survival follow-up may be enrolled in an extension study.

3.3 DURATION OF PARTICIPATION

Treatment will continue for 13 cycles, until disease progression per RECIST v1.1, or until unacceptable toxicity, whichever occurs first. The total duration of study participation for each individual is expected to range from 1 day to approximately 8 years.

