Patients whose tumors have a known *EGFR* mutation or *ALK* rearrangement will be excluded from enrollment in this study. Patients with tumors of non-squamous histology with unknown *EGFR* or *ALK* mutational status will be required to be tested prior to enrollment (see the specific inclusion criteria in Section 4.1.1). Patients with tumors of squamous histology who have an unknown *EGFR* or *ALK* mutational status will not be required to be tested (see the specific inclusion criteria in Section 4.1.1).

Patients must have histologically or cytologically documented NSCLC who present with locally advanced, unresectable (Stage III) disease (according to 8th revised edition of the AJCC [Amin et al. 2017]/UICC NSCLC staging system).

[REDACTED]

[figure not shown]
Eligible patients will be randomized in a 1:1 ratio to receive either atezolizumab plus tiragolumab or durvalumab.

Eligible patients will be stratified by ECOG Performance Status (0 vs. 1), PD-L1 expression, [REDACTED] tumor histology (non-squamous vs. squamous), and staging (Stage IIIA vs. Stage IIIB or IIIC).

In the experimental arm, atezolizumab will be administered to patients by IV infusion at a fixed dose of 1680 mg, followed by tiragolumab at a fixed dose of 840 mg administered by IV infusion on Day 1 of each 28-day cycle for a maximum of 13 cycles (see Figure 2).

In the comparator arm, patients will receive durvalumab 10 mg/kg Q2W administered by IV infusion on Days 1 and 15 of each 28-day cycle for a maximum of 13 cycles (not to exceed 26 doses) or fixed dose durvalumab at 1500 mg every 4 weeks (Q4W) (for patients whose weight \geq 30 kg), administered by IV infusion on Day 1 of each 28-day cycle for a maximum of 13 cycles (see Figure 2). [REDACTED]

Figure 2 Dosing Schedule for Experimental and Comparator Arms

D = day; Q2W = every 2 weeks; Q4W = every 4 weeks.

* On Day 15 of each 28-day cycle, patients in the comparator arm on Q2W durvalumab dosing will receive durvalumab 10 mg/kg IV.

** For patients whose weight ≥ 30 kg.

Treatment may be continued for 13 cycles, in the absence of metastatic disease, as long as patients are experiencing clinical benefit, as assessed by the investigator, in the absence of unacceptable toxicity or symptomatic deterioration attributed to disease progression after an integrated assessment of radiographic data, biopsy results (if available), and clinical status.

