to receive study treatment after apparent radiographic disease progression provided the benefit–risk ratio is judged to be favorable. Patients should be discontinued for metastatic disease, unacceptable toxicity or symptomatic deterioration attributed to disease progression, as determined by the investigator after an integrated assessment of radiographic data, biopsy results (if available), and clinical status (see Section 3.1.2).

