If a tumor assessment shows disease progression, it should be confirmed pathologically and/or by unequivocal radiographic evidence from the scan. If the scan shows equivocal findings (e.g., mediastinal nodes measure < 1.5 cm in the short axis, lung parenchymal lesions or visceral lesions measuring < 1 cm in the longest diameter), a biopsy should be performed. If a biopsy is not feasible or safe, then confirmatory scans should be performed no later than the next scheduled assessment, or earlier if clinically indicated. If a biopsy for disease progression confirmation is performed, any leftover biopsy tissue is strongly encouraged to be submitted for exploratory biomarker research (optional consent required for exploratory research; see [Section 4.5.8](#) for details). The biopsy should be performed prior to starting the next anti-cancer therapy. If the biopsy does not show evidence of disease progression (e.g., non-malignant infiltrates), then the patient may continue with scheduled study treatment, assessments, and/or follow-up.

Study treatment may be continued for 13 cycles of treatment, in the absence of metastatic disease, as long as patients are experiencing clinical benefit, as assessed by the investigator, and in the absence of unacceptable toxicity or symptomatic deterioration attributed to disease progression after an integrated assessment of radiographic data, biopsy results (if available), and clinical status. Patients who meet criteria for disease progression per RECIST v1.1 (see [Appendix 4](#)) will be permitted to continue treatment (atezolizumab plus tiragolumab or durvalumab) if they meet all of the criteria specified in Section [3.1.2](#).

After radiographic disease progression per RECIST v1.1 and discontinuation of study treatment, patients will undergo tumor assessments per local standard of care, as assessed by the investigator per RECIST v1.1, regardless of whether a patient starts a new anti-cancer therapy.

Scans will be submitted to the IRF for central review.

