4.6 TREATMENT, PATIENT, STUDY, AND SITE DISCONTINUATION

4.6.1 Study Treatment Discontinuation

Patients must permanently discontinue study treatment if they experience any of the following:

- Intolerable toxicity related to study treatment, including development of an immune-mediated adverse event determined by the investigator to be unacceptable given the individual patient's potential response to therapy and severity of the event
- Any medical condition that may jeopardize the patient's safety if he or she continues study treatment
- Investigator or Sponsor determination that treatment discontinuation is in the best interest of the patient
- Use of another non-protocol-specified anti-cancer therapy
- Pregnancy
- Loss of clinical benefit as determined by the investigator after an integrated assessment of radiographic and biochemical data, local biopsy results (if available), and clinical status (e.g., symptomatic deterioration such as pain secondary to disease) (see Section 3.1.2 for details)

The primary reason for study treatment discontinuation should be documented on the appropriate eCRF. Patients who discontinue study treatment prematurely will not be replaced.

Patients will return to the clinic for a treatment discontinuation/completion visit ≤ 30 days after the final dose of study treatment (see [Appendix 1](#)), regardless of whether they complete all 13 cycles or discontinue early. The visit at which response assessment shows progressive disease may be used as the treatment discontinuation/completion visit. Patients who discontinue study treatment for any

reason other than progressive disease or loss of clinical benefit will continue to undergo tumor response assessments and PRO assessments as outlined in the schedule of activities (see [Appendix 1](#)).

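### Section 3.3 stops study treatment at RECIST progression without exception, while the synopsis, five other protocol sections and the SAP allow conditional treatment past it; the mandatory-stop list in 4.6.1 does not name metastatic disease

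*Protocol*

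**What the plan says.** Protocol Section 3.3 (Duration of Participation) reads: "Treatment will continue for 13 cycles, until disease progression per RECIST v1.1, or until unacceptable toxicity, whichever occurs first". It contains no exception and no pointer to another section.

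Section 3.1.2 reads: "patients who meet criteria for disease progression per RECIST v1.1 and show evidence of clinical benefit may continue study treatment for up to 13 cycles". It sets four conditions that must all be met: investigator-assessed benefit, "Absence of metastatic disease", no symptoms or signs of unequivocal progression, and no ECOG decline attributable to progression.

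Other places follow 3.1.2:

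- Section 3.1.1: "Treatment may be continued for 13 cycles, in the absence of metastatic disease, as long as patients are experiencing clinical benefit". The synopsis and SAP Section 1.2 say the same. The synopsis does so under a Duration of Participation heading, the title that Section 3.3 carries.
- Section 3.4.10 explains why treatment past progression is allowed in both arms, and adds: "Patients should be discontinued for metastatic disease, unacceptable toxicity or symptomatic deterioration attributed to disease progression".
- Section 4.5.1 requires signed consent from patients who continue past progression.
- Section 4.5.6 says that patients with RECIST progression "will be permitted to continue treatment (atezolizumab plus tiragolumab or durvalumab) if they meet all of the criteria specified in Section" 3.1.2.

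Section 4.6.1 opens its mandatory list with: "Patients must permanently discontinue study treatment if they experience any of the following". The six items are intolerable toxicity, a medical condition that endangers the patient, an investigator or sponsor best-interest decision, other anti-cancer therapy, pregnancy, and loss of clinical benefit, the last with a reference to 3.1.2. Neither RECIST progression nor metastatic disease is an item.

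**The concern.** A stopping rule is an operative instruction. For a patient who progresses by RECIST but meets all the 3.1.2 conditions, Section 3.3 ends treatment and Section 3.1.2 permits it to continue. The consent step in 4.5.1 has no purpose if Section 3.3 governs.

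The list in 4.6.1, where a site would look for mandatory reasons to stop, does not settle the matter. It also leaves out a reason that 3.4.10 says should lead to discontinuation.

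Several data-collection rules are tied to the last dose or to whether treatment continues after progression. The conflict therefore affects what is measured, and when, as well as drug exposure.

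**Working it through.** The plan gives no figure to reproduce here. The check sets the passages side by side.

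**Step 1. Where the rules disagree, for a patient still on treatment**

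| Situation | Section 3.3 | Sections 3.1.2 / 3.4.10 | Section 4.6.1 |
|---|---|---|---|
| RECIST progression, all 3.1.2 criteria met | Stop | May continue | No named item applies |
| RECIST progression, investigator judges benefit lost | Stop | Stop | Stop |
| New metastatic disease, benefit not judged lost | Stop (new malignant lesions are progression in Appendix 4) | Stop | No named item applies, unless the best-interest item is invoked |
| Unacceptable toxicity | Stop | Stop | Stop |

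Row 1 is a direct contradiction. Row 3 is an omission: 3.3 and 3.1.2/3.4.10 agree, but the mandatory list is silent, because its reference to 3.1.2 sits inside the loss-of-benefit item. Section 4.6.1 is also uneven within itself. Its follow-up text treats progressive disease as a reason for discontinuation distinct from loss of clinical benefit, yet the list does not contain it.

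**Step 2. What depends on the rule, for row 1 patients**

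- *Exposure.* Treatment ends at progression or may run to Cycle 13.
- *Safety window.* Section 5.4.2.2 runs SAE reporting to 90 days after the final dose or new systemic anti-cancer therapy, whichever is first. It runs AESI reporting to 90 days after the final dose. Both windows move with the last dose.
- *PRO anchor.* Section 4.5.10.1 counts the 3- and 6-month assessments from RECIST progression or, for patients treated past progression, from loss of clinical benefit.
- *Scans.* Section 4.5.6 keeps patients treated past progression on the 8- or 12-weekly schedule until treatment stops. After progression and discontinuation, scans follow local standard of care, with no fixed interval.

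**Step 3. Link to the primary endpoint**

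PFS is assessed by the IRF, and patients without an event are censored at the last tumor assessment (Protocol 6.5.1, SAP 4.2.1). If the investigator calls progression before the IRF does, any later IRF progression depends on subsequent scans. Whether those keep the fixed schedule depends on whether treatment continued. Without treatment delays this can last at most through 13 × 28 = 364 days, or 52 weeks, from the first dose. The documents do not say how often the investigator precedes the IRF, so the effect cannot be sized.

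**Step 4. What does not depend on the rule**

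Survival follow-up continues about every 3 months after treatment, whatever the reason for stopping (Section 3.1.1). Early discontinuation is handled by treatment policy in the PFS and OS estimands (Table 1 of both documents), and the treatment attribute specifies only a maximum of 13 cycles.

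**The case against.** The strongest reply is that one summary sentence is out of step with a consistent body of text. The synopsis, the design section, the dedicated section on treatment after progression, the rationale, the consent procedure, the tumor-assessment section and the SAP all describe conditional continuation, and the consent, scan and PRO procedures are built around it. Most sites would probably meet those texts first. That is fair, and it limits the practical harm. It does not remove the contradiction, because Section 3.3 is an unqualified instruction with no cross-reference.

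Three stronger readings are tempting, and the documents do not support them.

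- *Three competing rules.* A reader might count 4.6.1 as a third rule. It is not one. Its loss-of-benefit item refers to 3.1.2, and a mandatory list that omits an item does not prevent a site from applying the 3.1.2 and 3.4.10 conditions. It is incomplete for one narrow case.
- *A large affected group.* A reader might take the 16.8-month durvalumab median PFS from Section 1.2.2 and work out how many patients have an event during 13 cycles. That would count deaths, patients already off treatment, and patients who stop under either rule. It would also use a result from the cited durvalumab trial, not a visible planning value of this one.
- *A difference between arms.* A reader might fear that sites in an open-label trial would apply different sections to the two arms. Sections 3.4.10 and 4.5.6 state continuation for both arms, and nothing in the documents points to differential use.

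**Conclusion.** The contradiction between Section 3.3 and the rest of the protocol and SAP is certain on the text. Both sets of passages are intact, and redaction does not explain it. The gap in 4.6.1 is real but narrow: new metastatic disease without a judgement of lost benefit.

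The affected patients are those still on treatment with RECIST progression who meet all four 3.1.2 criteria. Their number cannot be derived from the documents. For them, exposure, the final-dose safety window, the PRO anchor and the scan schedule depend on which section is applied. The scan schedule can affect IRF-PFS timing only when investigator-assessed progression comes first. The definitions of the primary and OS estimands, and survival follow-up, stand as written.

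This should be corrected because it is an operative instruction that cannot be followed as written and is easily repaired. It does not invalidate the primary analysis.

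**What to change.** Reconcile Sections 3.3, 3.1.1/3.1.2, 3.4.10, 4.5.6 and 4.6.1 so that one rule for treatment at progression is stated once and the other sections refer to it. In the same edit, make the mandatory list in 4.6.1 agree with that rule on both progression and metastatic disease, and check that the synopsis, Section 4.5.1 and SAP Section 1.2 match. Which clinical rule applies is for the sponsor to decide.

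If treatment past progression remains allowed, an optional by-arm summary of it can be added to the SAP exposure or disposition tables (SAP 4.5.1 and 4.6.1). The visible text there covers exposure and reasons for discontinuation, but does not separate treatment after progression.

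The cost is clarifying text in the protocol and at most one extra summary row. Sample size, endpoints and the main analysis are unchanged.

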3.4 RATIONALE FOR STUDY DESIGN

This Phase III study design is based on the hypothesis that the combination of atezolizumab plus tiragolumab following concurrent, platinum-based CRT without disease progression may prolong PFS compared with durvalumab in patients with locally advanced, unresectable Stage III NSCLC.

3.4.1 Rationale for Inclusion of Patients Independent of PD-L1 Status

Expression of PD-L1 is predictive for efficacy of PD1/PD-L1 inhibition in many cancers, including Stage III NSCLC (Antonia et al. 2017). Based on results of the Phase II GO40290 (CITYSCAPE) study, it may also be predictive for efficacy of combined therapy with tiragolumab plus atezolizumab in metastatic NSCLC in the absence of CRT or RT (see Section 1.6.2.3). However, the effects of cCRT may alter the tumor micro-environment and engage the immune system in ways that render PD-L1–negative tumors sensitive to this combination therapy (reviewed below in this section). It is therefore appropriate to evaluate the therapeutic potential of post-cCRT consolidation therapy with this combination in patients with Stage III NSCLC regardless of their PD-L1 status prior to CRT.

Durvalumab is the only standard of care therapy available for patients with locally advanced, unresectable Stage III NSCLC who have not progressed after definitive cCRT. All patients enrolled in this study will receive a PD-L1 inhibitor (durvalumab or atezolizumab), with patients in the experimental arm receiving tiragolumab also.

In the PACIFIC study, the efficacy of durvalumab consolidation therapy in a subgroup of PD-L1–evaluable patients (63% of the enrolled population) with PD-L1–negative patients (TC <1%) was analyzed retrospectively in a post-hoc unplanned analysis. In this relatively small subset of 90 patients who received durvalumab and 58 patients who received placebo based on the point estimate efficacy benefit was questionable, with an HR for PFS: 0.73; 95% CI: 0.48 to 1.11, and an HR for OS: 1.36; 95% CI: 0.79 to 2.34 (Borghaei et al. 2015; Antonia et al. 2018 [supplementary appendix]). Several lines of evidence support the hypothesis that the combination of tiragolumab and atezolizumab may confer improved efficacy outcomes in the PD-L1–negative subpopulation, as well as in the ITT population, when administered as consolidation therapy post-cCRT:

- In addition to direct cytotoxicity, CRT and RT have important effects on the tumor microenvironment and may potentiate the effects of CPIs. Cytotoxic CRT and RT result in increased release of tumor antigens, thereby enhancing tumor immunogenicity. Further, chemotherapeutic agents (Zhang et al. 2008) and RT

(Eastwood et al. 2013; Deng et al. 2014) have been shown to increase PD-L1 expression in human TCs in vitro and in vivo.

- It is now recognized that some effects of ionizing radiation act in an immune adjuvant fashion and engage the immune system resulting in tumor regression outside the radiation field—the abscopal effect (Formenti and Demaria 2013; Rodriguez-Ruiz et al. 2018).
- In addition, recent preclinical studies in mice bearing CT26 colon tumors, fractionated RT was shown to increase expression of TIGIT as well as of PD-L1 and to have additional effects on the tumor immune micro-environment that may be facilitative for combined immunotherapy with these two agents (Grapin et al. 2019).

Collectively, these observations indicate that CRT may increase tumor susceptibility to combined TIGIT and PD-L1 inhibition.

High unmet need remains in patients with Stage III unresectable NSCLC. Given the potential for CRT to increase tumor antigenicity, increase TIGIT and PD-L1 expression in the tumor, evaluation of the therapeutic potential of consolidation therapy with this combination requires testing in this clinical setting regardless of pre-CRT PD-L1 status. For this study, it is therefore proposed to randomize an all-comer population with respect to PD-L1 status and to stratify patients according to PD-L1 expression

Although PD-L1 inhibition provides a clinically meaningful benefit with consolidation therapy in patients with locally advanced, unresectable Stage III NSCLC (Antonia et al. 2018), the 5-year survival rate remains poor (Schild et al. 2019). Therefore, there is a continuing need for rational combinations with immunotherapies in order to broaden the patient population that may derive benefit and to deepen and extend response in the patient population that does respond.

TIGIT is a novel immune CPI that is often co-expressed with PD-L1 on tumor-infiltrating lymphocytes. In nonclinical models, combined blockade of both TIGIT and PD-L1/PD-1 pathways demonstrated superior efficacy over the respective single-agent treatments. It is hypothesized that the combination of an anti-TIGIT antibody, such as tiragolumab, with an anti-PD-L1/PD-1 antibody may result in activation of anti-tumor immune responses leading to enhanced killing of TCs and improved clinical responses.

Data from the randomized Phase II study (GO40290) indicate that combination therapy with tiragolumab and atezolizumab may confer an increased efficacy benefit in patients with untreated PD-L1-positive metastatic NSCLC relative to CPI therapy alone

(as discussed in Section 3.4.1). In patients with PD-L1 $\geq 1\%$, as determined using either the 22C3 IHC assay or the SP263 IHC assay, investigator-assessed PFS was improved in the tiragolumab plus atezolizumab arm (n=67) compared with that in the placebo plus atezolizumab arm (n=68) (stratified HR:0.57; 95% CI: 0.37 to 0.90; median PFS: 5.4 vs. 3.6 months, respectively). The data support the therapeutic hypothesis that tiragolumab and atezolizumab may further improve efficacy outcomes relative to durvalumab when administered as consolidation therapy for patients with locally advanced, unresectable Stage III NSCLC (refer to Section 3.4.1). To ensure adequate evaluation of this potential new therapy, the patient population in this study (GO41854) will be closely aligned with that in the PACIFIC study. Specifically, Study GO41854 will enroll male and female patients age ≥ 18 years old with ECOG Performance Status of 0 or 1 who have locally advanced, unresectable Stage III NSCLC (with staging determined according to the AJCC [8th revised version]/UICC NSCLC staging system) and who have not progressed following two prior cycles of concurrent platinum-based CRT.

